4.4 EXPLORATORY ENDPOINTS ANALYSIS

Exploratory endpoints detailed in Section 1.1.1.3 may also be analyzed. Binary endpoints will use similar statistical methods used for the primary endpoint (see Section 4.2.2) where appropriate. Missing data will be imputed using multiple imputations in the same approach as described in Section 4.2.2, where applicable.

For CRR including urinary sediment, RBC, and RBC cast will be imputed from the previous scheduled visit by single imputation similar to the approach described in Section 4.2.3. If RBC cast is missing at the previous visit, it will be imputed as non RBC cast. If RBC is missing at the previous visit, the patient will be considered as non-responder. UPCR and eGFR will be imputed from previous visits as described in Section 4.2.3.

Continuous endpoints will be summarized using descriptive statistics or analyzed using similar statistical methods used for the continuous endpoints in Section 4.2.3, where appropriate.

eGFR slope through Week 76 will be analyzed using mixed effect model with random intercept and random slope.

Time-to-event endpoints will be analyzed similarly to the time to onset of CRR (Section 4.3.2.4), where appropriate. Patients who do not experience the events of interest will be censored at the last known date of not experiencing the events.

Additionally, descriptive comparisons of the obinutuzumab treatment groups (obinutuzumab Arm 1 [2-2-2 Regimen] and obinutuzumab Arm 2 [2-2-1 Regimen]) will be performed on the basis of the primary and the key secondary endpoints.

Further analysis details with post Week 76 blinded treatment period data are provided in Section 4.6.6.

4.5 SAFETY ANALYSES

The safety analyses will be performed on the safety-evaluable population as defined in Section 3.1.3 with data collected in the Week 76 treatment period for each patient. Safety outputs will include data until the point of rescue for the patients who receive rescue therapy (excluding corticosteroid rescue). Limited key safety outputs will be produced for post-rescue data.

Safety data will be summarized by the obinutuzumab (combined treatment groups) and placebo groups. Additionally, combined obinutuzumab treatment group will be further broken down to obinutuzumab arm 1 (2-2-2 regimen) and obinutuzumab arm 2 (2-2-1 regimen) for selected key safety data up to Week 76.

Additional analysis including post Week 76 data collected till CCOD will be produced. The post Week 76 analysis details are provided in Section 4.6.7.

4.5.1 Extent of Exposure

A summary of exposure to study treatment will be produced using the dose recorded on the electronic Case Report Form (eCRF). The number of blinded obinutuzumab infusions and treatment duration will be summarized. Obinutuzumab treatment duration will be calculated as difference between date of last dose and date of first dose plus one day.

MMF exposure will be summarized using treatment duration and total cumulative dose.

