4.4.4 Rescue Therapy and Treatment Failure

4.4.4.1 Rescue Therapy

Disease flares may be managed with temporary increases in corticosteroid doses while continuing the study treatment regimen (see Appendix 5). In some cases of worsening or severely active disease, the investigator may conclude that the patient has failed the randomized treatment regimen and requires rescue therapy. The randomized treatment assignment will not be unblinded at the time of rescue therapy. Therapies that are considered rescue include the following:

- Cyclophosphamide
- Anti-CD20 antibodies, including rituximab, ocrelizumab, ofatumumab, and obinutuzumab (if given outside the study protocol)
- Calcineurin inhibitors including ciclosporin, tacrolimus, and voclosporin
- Other investigational, biologic, or targeted therapies used for the treatment of SLE or LN

Because these rescue therapies may affect subsequent efficacy assessments, patients who receive rescue will be treated as nonresponders for subsequent efficacy analyses.

Because the safety of obinutuzumab in combination with these rescue therapies has not been studied, patients who receive rescue will discontinue obinutuzumab or placebo infusions and will not be eligible for open-label treatment (see exception for corticosteroid-only rescue, Section 4.4.4.1.1 below). These patients will continue to be followed according to the study schedule of activities through Week 76 and for at least 12 months from the last dose of obinutuzumab or placebo (see Section 3.1.4).

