6.4 SAFETY ANALYSES

The safety-evaluable population is defined as patients who received any part of blinded infusion of obinutuzumab or placebo. Patients who were randomized to the study but who did not receive any part of blinded infusion of obinutuzumab or placebo will not be included in the safety population. Patients will be grouped according to the treatment that patients actually received rather than the treatment assigned. Patients who received any part of an infusion of obinutuzumab even if not assigned to obinutuzumab treatment group at randomization will be reported under the obinutuzumab treatment group. All safety analyses will be performed using the safety-evaluable population.

Safety will be assessed through summaries of exposure to study treatment, adverse events, adverse events in relation to ADAs, adverse events in relation to B-cell depletion and low Ig, changes in laboratory test results, and changes in vital signs and ECGs.

Study treatment exposure (such as treatment duration, total dose received, and dose modifications) will be summarized with descriptive statistics.

All verbatim adverse event terms will be mapped to Medical Dictionary for Regulatory Activities (MedDRA) thesaurus terms, and adverse event severity will be graded according to NCI CTCAE v5.0. All adverse events, serious adverse events, adverse events leading to death, adverse events of special interest, and adverse events leading to study treatment discontinuation that occur on or after the first dose of study treatment (i.e., treatment-emergent adverse events) will be summarized by mapped term, appropriate thesaurus level, and severity grade. For events of varying severity, the highest grade will be used in the summaries. Deaths and cause of death will be summarized.

Relevant laboratory, vital sign (pulse rate, respiratory rate, blood pressure, pulse oximetry, and temperature), and ECG abnormalities will be displayed by time, with grades identified where appropriate. Additionally, a shift table of selected laboratory tests will be used to summarize the baseline and maximum postbaseline severity grade. Changes in vital signs will be summarized.

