3.1 ANALYSIS POPULATIONS

3.1.1 Randomized Population

The randomized population will include all patients randomized into the study.

3.1.2 Efficacy-Evaluable Population

Efficacy-evaluable population will consist of all randomized patients regardless of whether they received study drug. Patients will be grouped according to randomized (assigned) treatment, rather than treatment received. Patients who received an incorrect therapy will be reported under the treatment group to which they were randomized. All efficacy analyses will be performed using the efficacy-evaluable population.

3.1.3 Safety-Evaluable Population

The safety-evaluable population is defined as patients who received any part of blinded infusion of obinutuzumab or placebo. Patients who were randomized to the study but who did not receive any part of blinded infusion of obinutuzumab or placebo will not be included in the safety population. Patients will be grouped according to the treatment that patients actually received rather than the treatment assigned. Patients who received any part of an infusion of obinutuzumab as a study treatment (excluding obinutuzumab infusion received as a rescue therapy) even if not assigned to obinutuzumab treatment group at randomization will be reported under the obinutuzumab treatment group.

All safety analyses will be performed using the safety-evaluable population.

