4.5.2 Adverse Events

All verbatim AEs terms will be coded using the latest version of Medical Dictionary for Regulatory Activities (MedDRA).

For safety analyses, unless otherwise specified, only treatment-emergent AEs will be included in the analyses. Treatment-emergent AEs will be defined as any new AEs reported or any worsening of an existing condition on or after the infusion of Obinutuzumab or placebo post randomization (excluding AEs reported in the eCRF as occurred prior to the first study drug administration) through the completion of the study

or until a patient discontinues study prematurely. Adverse events with missing onset date will be considered to be treatment emergent. Adverse events with partially missing onset date will also be included as treatment emergent when the month (if it was recorded) and the year occur on or later than the month and year of the study treatment start date.

AEs will be summarized by system organ class (SOC) and preferred term (PT), and will be presented in order of descending frequency summed across the treatment groups within each SOC and PT. For each treatment group, the incidence count for each AE PT will be defined as the number of patients reporting at least one treatment-emergent occurrence of the event (multiple occurrences of the same AE in 1 patient will be counted only once). The proportion of patients with an AE will be calculated as the incidence count divided by the total number of patients in the population. Each table will also present the total number of AEs reported where multiple occurrences of the same AE in an individual are counted separately.

The following will be summarized, and/or listings produced where required:

- All AEs
- SAEs
- AEs by relationship to obinutuzumab/placebo
- AEs by relationship to MMF
- AEs leading to blinded obinutuzumab discontinuation
- AEs leading to MMF discontinuation
- AEs by NCI CTCAE grade
- Infections
- Serious Infections
- Adverse events of special interest (AESIs) as defined in Section 5.2.3 of the protocol
 - Infusion Related Reactions (IRRs)
 - Grade 3–5 infections
 - Any hepatitis B reactivation or Progressive Multifocal Leukoencephalopathy (PML)
 - Drug-related neutropenia
 - Drug-related thrombocytopenia
 - Gastrointestinal perforations
 - Worsening of pre-existing cardiac conditions

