 - Cases of potential drug-induced liver injury that include an elevated ALT or AST in combination with either an elevated bilirubin or clinical jaundice, as defined by Hy's Law

- Suspected transmission of an infectious agent by the study drug
- AEs leading to study discontinuation
- AEs leading to death
- AEs leading to blinded obinutuzumab dose interruption
- AEs leading to MMF dose modification or interruption
- COVID-19 AEs

For key safety events, the AE rates per 100 patient-years exposure will be calculated with 95% CIs by treatment groups, using all occurrences of adverse events. The rate of AEs per 100 patient years is calculated as:

(Total Number of AEs/Total Number of Patient Years at Risk)×100

All summaries and listings of AEs will be listed in the List of Planned Outputs (LoPO).

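### The crude safety tables stop at non-steroid rescue but keep rescued patients in the denominator, so they understate risk more in whichever arm has more rescue

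*SAP*

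**What the plan says.** SAP 4.5 limits the main safety analyses to the 76-week treatment period and adds a second limit: "Safety outputs will include data until the point of rescue for the patients who receive rescue therapy (excluding corticosteroid rescue". The next sentence reads "Limited key safety outputs will be produced for post-rescue data". It does not say which outputs these are, or whether they compare the arms over the whole 76 weeks.

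The denominator is not shortened to match. SAP 4.5.2 states: "The proportion of patients with an AE will be calculated as the incidence count divided by the total number of patients in the population". SAP 3.1.3 defines that population without reference to rescue: "The safety-evaluable population is defined as patients who received any part of blinded infusion of obinutuzumab or placebo". The outputs listed in 4.5.2 include SAEs, serious infections, Grade 3-5 infections and the other AESIs, and "AEs leading to death". For key safety events 4.5.2 also plans rates per 100 patient-years with 95% CIs, but it does not say when time at risk ends.

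Protocol 6.4 plans summaries of adverse events "that occur on or after the first dose of study treatment (i.e., treatment-emergent adverse events) will be summarized", and of deaths, and mentions no stop at rescue. On rescued patients, Protocol 4.4.4.1 says: "These patients will continue to be followed according to the study schedule of activities through Week 76". SAP Appendix 1, which lists changes from the protocol-planned analyses, covers only the time points of some exploratory response endpoints.

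**The concern.** A rescued patient whose first SAE, serious infection or fatal event comes after rescue counts as a patient at risk for 76 weeks who had no event. Rescue follows worsening or severely active disease, so it is a post-randomisation outcome of the treatments being compared. If the arms are rescued at different rates, follow-up is cut unequally and for reasons linked to prognosis. The crude proportions then no longer compare the arms over a common period.

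The data needed to avoid this will exist. Rescued patients stay on the visit schedule through Week 76, adverse events are recorded at each of those visits, and Protocol 5.3.1 requires adverse event reporting for at least 12 months after the last infusion. Protocol 4.4.4.1 also notes that obinutuzumab combined with the rescue drugs has not been studied for safety. The main tables would leave out the period in which such combined exposure occurs.

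**Working it through.** **Figures available.** The plan gives no rescue rate, rescue timing or post-rescue event rate, so it has no figure of its own to reproduce on this point. Its one design calculation does reproduce, although nothing here depends on it. With 126 per arm and 50% vs 30% CRR, power = Φ[(0.20 − 1.96 × √(2 × 0.4 × 0.6/126)) / √((0.25 + 0.21)/126)] = Φ[(0.20 − 0.1210)/0.0604] = Φ(1.31) ≈ 0.905, against the stated 90%.

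**Inputs from the documents.** 126 per arm (SAP 2.2) and a 76-week window (SAP 4.5). For scale only, the phase II incidences by Week 76 for obinutuzumab vs placebo were 23% vs 30% for SAEs and 2% vs 7% for deaths (Protocol 1.3).

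**Assumptions.** Constant event hazard before rescue, the same in both arms. Rescue fraction r, with rescue time t uniform over Weeks 24-76. Hazard multiplied by m after rescue.

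**Formulas.** Let P be the 76-week risk without rescue and λ = −ln(1 − P)/76.
- Shown in the tables: C = (1 − r)P + rA, where A is the mean of 1 − exp(−λt).
- All events to Week 76: T = (1 − r)P + rB, where B is the mean of 1 − exp(−λt − mλ(76 − t)).
- Missed: T − C = r(B − A).

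C does not contain m, so the truncated table looks the same whatever happens after rescue. The missed risk rises with r. The arm with more rescue therefore loses more, provided rescue timing and post-rescue risk are similar in the two arms.

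**Numbers for P = 0.30.** λ = 0.3567/76 = 0.004693 per week.
- A = 1 − (e^(−24λ) − e^(−76λ))/(52λ) = 1 − (0.8935 − 0.7000)/0.2440 = 0.207
- B = 0.300 for m = 1
- B = 1 − 0.343 × (2.0408 − 1.2527)/0.4881 = 0.446 for m = 3

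For r = 10%, C = 0.27 + 0.0207 = 29.1%. For r = 30%, C = 0.21 + 0.0621 = 27.2%. With m = 3, T = 0.27 + 0.0446 = 31.5% and 0.21 + 0.1339 = 34.4%.

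| Rescue in the two arms | Hazard after rescue | Shown | All events | Shift in difference |
|---|---|---|---|---|
| 10% / 20% | unchanged | 29.1% / 28.1% | 30.0% / 30.0% | 0.9 points |
| 10% / 30% | unchanged | 29.1% / 27.2% | 30.0% / 30.0% | 1.9 points |
| 10% / 30% | doubled | 29.1% / 27.2% | 30.8% / 32.4% | 3.4 points |
| 10% / 30% | tripled | 29.1% / 27.2% | 31.5% / 34.4% | 4.8 points |

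In the last two rows the order of the arms reverses. Over rescue of 5%/10% to 10%/30%, m from 1 to 3, and P of 23% or 30%, the SAE shift is 0.4 to 4.8 points (up to 6.8 if rescue can occur from Day 1). SAE patients missed per 126 are about 0.5 to 3 in the lower-rescue arm and 0.9 to 9 in the other. For deaths (P of 2% or 7%) the shift is 0.03 to 1.4 points.

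**Direction if placebo is rescued more.** Assume P = 12%, rescue at Week 40 in 20% of placebo and 8% of obinutuzumab patients, and hazard doubled afterwards. The risk to Week 40 is 6.51%, and the 76-week risk in rescued patients is 17.17%.
- Truncated: placebo 0.8 × 12 + 0.2 × 6.51 = 10.90%; obinutuzumab 0.92 × 12 + 0.08 × 6.51 = 11.56%; ratio 1.06.
- All events: placebo 9.60 + 3.43 = 13.03%; obinutuzumab 11.04 + 1.37 = 12.41%; ratio 0.95.

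**Patient-year rates.** Mean rescue time is (24 + 76)/2 = Week 50, so a rescued patient loses 26 of 76 weeks of counted data. If the time at risk still ran to Week 76, a constant rate would be understated by 0.10 × 26/76 = 3.4% in one arm and 0.30 × 26/76 = 10.3% in the other. If it ends at rescue, this error goes, but any rise in risk after rescue is still unseen.

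**All Exposure analysis (SAP 4.6.7).** Rescue is among the events that end an obinutuzumab patient's contribution. It is not among those listed for placebo.

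**The case against.** The strongest defence is that stopping at rescue is a legitimate on-treatment view. Non-steroid rescue ends the blinded infusions, and later events mix in another drug. This stands as a reason to keep the truncated tables, and which view is called main is arguable. It does not justify dividing truncated counts by patients treated as followed to Week 76.

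The plan also has partial safeguards. Post-rescue outputs are promised, patient-year rates are planned for key events, deaths through Week 76 enter a key secondary endpoint (SAP 4.3.1.4), and the iDMC sees unblinded safety data throughout. But the post-rescue outputs are not specified, the end of time at risk is undefined, and the secondary endpoint pools deaths with renal events and does not cover SAEs or infections.

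Precision also limits the point. At 12% risk and 126 per arm, the standard error of the log risk ratio is √(2 × 0.88/(126 × 0.12)) = 0.341. The 95% CI then spans a factor of exp(1.96 × 0.341) ≈ 1.95 either way, wider than the move from 0.95 to 1.06.

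A reader might infer that the cut contradicts Protocol 6.4 and the SAP's own treatment-emergent definition, which runs "through the completion of the study". That is too strong. Neither text mentions rescue. The quoted protocol line fixes when counting starts, and the SAP definition classifies events and does not set the data window of a table. What can be said is that the protocol announced no such stop and that Appendix 1 does not record one.

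**Conclusion.** The point holds for the crude incidence tables: as written, they omit post-rescue events while keeping rescued patients in the denominator. With similar rescue timing and post-rescue risk in the two arms, this understates risk more in the arm with more rescue. The size rests wholly on assumed rescue rates and hazards. It is small if risk does not rise after rescue (0.4 to 1.9 points for SAEs with rescue from Week 24) and a few points if it does.

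Two stronger readings are not supported. One is that the cut flatters obinutuzumab. No rescue rates are given, and if placebo is rescued more, as a working drug would suggest, the cut makes obinutuzumab look relatively worse. The other is that post-rescue deaths and SAEs will go unreported. The SAP promises some post-rescue outputs and leaves their content open. The gap is the absence of a stated by-arm comparison over the full 76 weeks. It is worth correcting, at modest severity.

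**What to change.** In SAP 4.5, add by-arm tables of deaths, SAEs, serious infections, Grade 3-5 infections and AESIs that use all data through Week 76 regardless of rescue, shown beside the rescue-truncated tables. In addition:

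- Name the post-rescue outputs.
- In SAP 4.5.2, state that patient-years at risk end at rescue for truncated outputs and at the end of the Week 76 period (or earlier withdrawal or death) for untruncated ones.
- In SAP 4.6.7, apply the same rescue stop rule to both arms.
- List the truncation in Appendix 1.

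The cost is a few sentences and one extra set of key tables from data already being collected. The downside is that some post-rescue events in the added tables will reflect the rescue drug. The truncated tables beside them let a reader see how much this matters.

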5.1.1 Risks Associated with Obinutuzumab

5.1.1.1 Infusion-Related Reactions

The most frequently observed adverse drug reactions in patients who received obinutuzumab during clinical studies in CLL and NHL were IRRs, which occurred predominantly during infusion of the first 1000 mg. In patients who received the combined measures for prevention of IRRs (adequate glucocorticoid, oral analgesic/antihistamine, omission of antihypertensive medication in the morning of the first infusion, and, for CLL patients only, the Cycle 1 Day 1 dose administered over 2 days), a decreased incidence of all grade IRRs was observed. The rates of Grades 3–4 IRRs (which were based on a relatively small number of patients) were similar before and after mitigation measures were implemented. The incidence and severity of infusion-related symptoms decreased substantially after the first 1000 mg was infused, with most patients having no IRRs during subsequent administrations of obinutuzumab.

In the majority of patients, IRRs were mild to moderate and could be managed by the slowing or temporary halting of the first infusion, but severe and life-threatening IRRs requiring symptomatic treatment have also been reported. IRRs may be clinically indistinguishable from IgE-mediated allergic reactions (e.g., anaphylaxis).

In studies where patients received either obinutuzumab or rituximab (another anti-CD20 monoclonal antibody), obinutuzumab patients appeared to have more IRRs compared to those receiving rituximab in patients being treated for hematologic malignancies.

In the NOBILITY study, at the Week 76 data cut, obinutuzumab was associated with increased non-serious infusion-related reactions (16% obinutuzumab vs. 10% placebo). All IRRs in obinutuzumab arm were non-serious. Of the 10 patients, the IRRs occurred at the first infusion in 8 patients; all IRRs resolved and none led to obinutuzumab discontinuation.

Details regarding management of IRRs can be found in Section 5.1.3.

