Additional renal biopsy (optional) bb												Х	X b	

Table 1 Schedule of Activities through Week 76 (cont.)

ADA=anti-drug antibody; CT=computed tomography; eCRF=electronic Case Report Form; EQ-5D-5L=EuroQol 5-Dimension, 5-Level Questionnaire; FACIT-F=Functional Assessment of Chronic Illness Therapy–Fatigue; HBcAb=hepatitis B core antibody; HBsAg=hepatitis B surface antigen; HBV=hepatitis B virus; HCV=hepatitis C virus; IxRS=interactive Web response system; MMF=mycophenolate mofetil; PGA=Physician's Global Assessment; PK=pharmacokinetic; SF-36 v2=36-Item Short Form Survey, Version 2; SGA=Subject's Global Assessment; SLEDAI-2K=Systemic Lupus Erythematosus Disease Activity Index 2000; UPCR=urinary protein-to-creatinine ratio.

Notes: All assessments will be performed pre-infusion unless otherwise specified. Visits except for Day 1 should be performed within ±3 days of the scheduled visit. However, an interval of 14 days should be kept between paired blinded obinutuzumab infusions (Days 1 & 14 (Week 2); Days 168 (Week 24) & 182 (Week 26); Days 350 (Week 50) & 364 (Week 52)), i.e. second of a course of two 6 monthly infusions interspersed by 2 weeks ('paired infusions').

- a At screening, IxRS will be contacted to obtain assignment of patient screening number. This will be the start of the 28 day screening window. At the discretion of the Medical Monitor, the maximum screening window of 28 days may be extended by up to 7 additional days to permit completion of subject eligibility assessment. At Day 1, IxRS will be contacted to obtain patient randomization number and drug assignment.
- Unplanned visits may be performed if clinically indicated. Adverse events, concomitant medications and vital signs must be assessed for each unplanned visit. Other procedures, tests, and assessments will be performed at the discretion of the investigator. However, in case of a change in lupus symptomatology or a suspected flare, the following tests should be performed for study purposes: urinalysis including UPCR, chemistry panel, hematology panel, flow cytometry, clinician reported outcomes (PGA and SLEDAI-2K), autoantibodies, complement C3 and C4 as well as samples for pharmacokinetics and ADA assessments. Any unplanned laboratory samples should also be sent to the central laboratory per instructions in the laboratory manual.
- Patient-reported outcomes will be performed prior to other assessments and procedures.

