Patients will be randomized to receive obinutuzumab or placebo in a 1:1 ratio. Patients randomized to receive obinutuzumab will be further randomized to receive one of the two obinutuzumab dosing schedules in a 1:1 ratio:

- Obinutuzumab Arm 1 (2-2-2 Regimen): absolute (flat) dose of 1000 mg IV on Day 1 and Weeks 2, 24, 26, 50, and 52
- Obinutuzumab Arm 2 (2-2-1 Regimen): absolute (flat) dose of 1000 mg IV on Day 1 and Weeks 2, 24, 26, and 52

All patients will receive blinded infusions on Day 1 and Weeks 2, 24, 26, 50, and 52.

The randomization of patients into treatment and control groups will be managed by a central IxRS vendor and will be performed by stratified block design—stratified by region and race as follows:

- Region
 - United States and Canada
 - Latin America and the Caribbean
 - Other
- Race
 - Black
 - Other

These stratification factors were selected given expected differences in response by region and race. LN is clinically heterogeneous in presentation and factors such as availability and intensity of standard of care therapies; socioeconomic status; and ethnicity are known to affect a patient's response to treatment (Tesar et al. 2011). In particular, black race is associated with more aggressive disease (Korbet et al. 2007).

Because it is important to maintain blinding to preserve the integrity of the data collected, all laboratory studies of blood specimens, with unblinding potential, will be performed by a central laboratory. Therefore, site personnel and the Sponsor's staff involved with the conduct of the study will not receive unblinded data related to peripheral B-cell counts, PK results, specific immunoglobulin levels, or ADA results during the study, as listed below, until the primary efficacy and safety analyses through Week 76.

While PK samples must be collected from patients assigned to the comparator arm to maintain the blinding of treatment assignment, PK assay results for these patients are generally not needed for the safe conduct or proper interpretation of this study. Sponsor personnel responsible for performing PK assays will be unblinded to patients' treatment assignments to identify appropriate PK samples to be analyzed. Samples from patients who are assigned to the comparator arm will not be analyzed except by request (e.g., to evaluate a possible error in dosing).

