If the change in eGFR is significant, the unused alpha (either 0.05 or 0.01 depending on whether the proteinuric response endpoint was significant) will be passed to the next endpoints in the sequence and each endpoint will be tested sequentially after achieving the statistical significance on the previous endpoint. Testing stops as soon as there is a failure of an endpoint in the following sequence to show significance. The endpoints after the non-significant endpoint in the sequence will be deemed non-significant.

- 4. Proportion of patients who experience death or renal-related events through Week 76
- 5. Proportion of patients who achieve an ORR evaluated at Week 50
- 6. Change in FACIT-F scale from baseline to Week 76

The fallback method described above is also depicted in Figure 2.

Figure 2 Multiplicity Adjustment Using Fallback Method

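### By-arm safety tables count from Day 1 and by-arm efficacy includes ORR at Week 50, although the two obinutuzumab regimens are identical until the Week 50 infusion

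*SAP*

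**What the plan says.** **Regimens.** SAP 1.2.1 gives Arm 1 obinutuzumab 1000 mg on Day 1 and Weeks 2, 24, 26, 50 and 52. The second arm is "Obinutuzumab Arm 2 (2-2-1 Regimen): absolute (flat) dose of 1000 mg IV on Day 1 and Weeks 2, 24, 26, and 52". Protocol 3.3.1 states that Arm 2 receives placebo at Week 50, so that infusion is the only planned difference through Week 76.

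**Safety by arm.** SAP 4.5 reports the combined group against placebo, then separates "obinutuzumab arm 1 (2-2-2 regimen) and obinutuzumab arm 2 (2-2-1 regimen) for selected key safety data up to Week 76". SAP 4.5.2 counts treatment-emergent events "on or after the infusion of Obinutuzumab or placebo post randomization". No later start is given for the by-arm breakdown.

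**Efficacy by arm.** SAP 4.4 says the descriptive comparison of the arms will be "performed on the basis of the primary and the key secondary endpoints". SAP 2.1.1 lists six key secondaries, one of which is "Proportion of patients who achieve an ORR evaluated at Week 50". Another, death or renal-related events, accumulates over all visits through Week 76 (SAP 4.3.1.4).

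**Timing at infusion visits.** The notes to Table 1 in Protocol Appendix 1 state: "All assessments will be performed pre-infusion unless otherwise specified".

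**Status.** Protocol 3.3.1 makes the arm comparison descriptive only and expects no difference in renal response at Week 76. It says the two schedules are there to provide pharmacokinetic and pharmacodynamic data in support of chronic dosing.

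**The concern.** A comparison of two regimens can only be informative after they diverge. Before Week 50, any difference between Arms 1 and 2 is chance, because treatment is identical and blinded. Safety tables that start on Day 1 mix a long common period with a short informative one. This pulls ratios toward 1 and adds noise. ORR at Week 50 is worse placed, because the whole outcome precedes the only differing infusion.

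The SAP specifies no other by-arm clinical safety analysis. The All Exposure analysis in SAP 4.6.7 pools obinutuzumab patients and also starts at the first dose. The Day 1 to Week 76 table is thus the only specified by-arm view of clinical safety for one versus two Month 12 infusions. Two misreadings are possible: an excess of, say, infections after the second Month 12 infusion looks smaller than it is, or a chance imbalance in early events or in Week 50 ORR is taken for a regimen effect. No test or error control accompanies these tables to guard against either.

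**Working it through.** **The plan's own figure.** The only stated power is for combined obinutuzumab versus placebo: 126 per group, CRR 50% versus 30%, two-sided 0.05, about 90% (Protocol 6.1, SAP 2.2). With pooled variance under the null:

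Φ[(0.20 − 1.96·√(2·0.4·0.6/126)) / √((0.3·0.7 + 0.5·0.5)/126)] = Φ[(0.20 − 0.121)/0.0604] = Φ(1.31) ≈ 0.905.

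The figure reproduces. The documents give no power or precision for Arm 1 versus Arm 2.

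**Inputs for the arm comparison**
- Week 50 is Day 350 and Week 76 is Day 532 (Protocol Appendix 1, Table 1).
- 1:1 split of 126 gives about 63 per arm.
- Assumed, since the documents give no values: constant event rate, independent (Poisson) events, no dropout, and the rates and ratios shown.

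**Share of common treatment.** 350/532 = 65.8%, leaving 182/532 = 34.2% that can differ. Person-years per arm: 63 × 532/365.25 = 91.8 in total, and 63 × 182/365.25 = 31.4 after Week 50.

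**Attenuation of the rate ratio.** Whole-period ratio = (350 + 182 × RR)/532.

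| True post-Week 50 ratio | Ratio seen from Day 1 |
|---|---|
| 1.25 | 1.09 |
| 1.5 | 1.17 |
| 2.0 | 1.34 |
| 3.0 | 1.68 |

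**Signal against noise.** Take a ratio of 2.0 and z = ln(ratio)/√(1/E1 + 1/E2), where E1 and E2 are the expected events in Arms 1 and 2.

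| Assumed Arm 2 rate per patient-year | E1, E2 from Day 1 | z | E1, E2 from Week 50 | z |
|---|---|---|---|---|
| 1.0 | 123.2, 91.8 | 2.13 | 62.8, 31.4 | 3.17 |
| 0.3 | 36.9, 27.5 | 1.17 | 18.8, 9.4 | 1.74 |

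At the higher rate the absolute difference is 31.4 events in both windows (123.2 − 91.8 and 62.8 − 31.4). Its standard error is √215.0 = 14.7 from Day 1 and √94.2 = 9.7 from Week 50.

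**Patient incidence.** SAP 4.5.2 counts each patient once per event term, so a patient with an early event adds nothing after the split. Protocol 5.1.1.2 reports infections in 70% of obinutuzumab patients at the NOBILITY Week 76 cut. Assume the same risk in Arm 2 and a constant hazard. By Week 50, 1 − 0.30^(350/532) = 55% are already counted. A post-Week 50 hazard ratio of 2 then gives 80% versus 70% over the whole period (risk ratio 1.14). Counting onsets from Week 50 gives 56% versus 34% (1.66).

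**Infusion-related reactions.** These cluster earlier than a constant rate implies. In NOBILITY, "Of the 10 patients, the IRRs occurred at the first infusion in 8 patients", and both arms share that infusion.

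**Efficacy endpoints by arm**
- Wholly before the split: ORR at Week 50 (1 of 7).
- Partly before it: death or renal-related events through Week 76 (1 of 7).
- Assessed at Week 76: CRR, CRR with prednisone taper, proteinuric response, eGFR change and FACIT-F change (5 of 7).

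Under the midpoint visit windows in SAP 4, a few Week 50 values could fall after the infusion. The value nearest the scheduled day is used, so this changes little.

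**Precision.** With 63 per arm and CRR near 50%, the 95% half-width for the difference is 1.96 × √(2 × 0.25/63) = 0.175, about 17 points. A difference of about 25 points would be needed for 80% power.

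**The case against.** The strongest reply is that this is a descriptive breakdown with no hypothesis, no alpha and no expected difference in renal response. That is correct, and nothing here touches the primary or key secondary tests.

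A reader might infer that most of the regimen comparison sets a treatment against itself. The documents do not support that for efficacy: five of seven endpoints are assessed at Week 76, 26 weeks after the split. The statement holds only for safety follow-up time.

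A reader might also infer that a regimen effect would be hidden. It would not be. Events before the split cancel in expectation, so the absolute difference in total event counts survives, and SAP 4.5.2 does tabulate total counts. What suffers is the ratio, the once-per-patient incidence and the noise.

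Three further points stand in part:
- The individual adverse event outputs sit in a List of Planned Outputs that is not among the documents. A windowed table there cannot be ruled out, but the SAP text does not call for one.
- Protocol 2.1.3 bases the arm comparison on the renal response endpoints, which include ORR at Week 76. The SAP narrows this to the primary and key secondary endpoints, and SAP Appendix 1 does not list the narrowing as a change. This supports the replacement proposed for ORR.
- Restarting the death or renal-related endpoint at Week 50 would be more than a date filter. Worsening proteinuria uses 24-hour UPCR at Weeks 24, 50 and 76, so one scheduled assessment remains after the split. The endpoint also runs through multiple imputation, and efficacy analyses use all randomised patients.

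**Conclusion.** The concern holds within limits. About 66% of by-arm safety follow-up is identical treatment, and the plan specifies no by-arm view of the period in which the regimens differ. A true rate ratio of 1.5 or 2.0 after Week 50 would appear as about 1.17 or 1.34. Those figures assume a constant event rate and illustrative ratios; the 350 of 532 days comes from the schedule. ORR at Week 50 has no regimen content because it precedes the differing infusion. The cumulative death or renal-related endpoint is diluted but still interpretable.

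The five Week 76 endpoints remain valid contrasts of the assigned regimens, and the comparison of obinutuzumab with placebo is unaffected. Small numbers limit the arm comparison whatever window is used.

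**What to change.** 1. **SAP 4.5.** Add by-arm tables of the key adverse events with onset from the blinded Week 50 infusion through Week 76, in patients who received that infusion, with person-time starting on that date. Treatment is identical and blinded until then, so receiving the infusion cannot depend on regimen and the contrast stays randomised. Keep the whole-period tables as background.
2. **SAP 4.4.** For Arm 1 versus Arm 2 only, use ORR at Week 76 (already an exploratory endpoint in SAP 1.1.1.3) in place of ORR at Week 50. The key secondary endpoint against placebo does not change.
3. **Death or renal-related events.** Leave the endpoint as defined, in all randomised patients. Add a note that it includes 50 weeks of common treatment and, optionally, list events with onset after Week 50 by arm.

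The cost is a few sentences in the SAP, a date filter on existing safety tables and one by-arm summary of an endpoint already defined. The downside is fewer patients and events in the window: at most 31.4 of 91.8 person-years per arm, and less once patients who stop before Week 50 are left out. The tables should be labelled descriptive and imprecise.
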